2.1 RATIONALE AND SPECIFIC AIMS

There are many other medications that may reduce irritability and aggression, and thus, this effort is only part of an ongoing, systematic approach to build an evidence-base to guide informed decision making. The investigators are committed to studying the effect of additional medications in the future, as well as continuing comprehensive, systematic study of post-TBI irritability and aggression. The current work fits additional pieces into a complex puzzle to address the treatment of these problematic behaviors. This body of work supports the priorities of the NIDRR Long-Range Plan⁷⁰ through the production of new scientific knowledge through research into pharmacologic interventions that can be used to improve options for achieving independence, social involvement, and function.

Primary Aim: Assess treatment effects of buspirone (BUSP) on TBI irritability/aggression

Primary Hypothesis (Hypothesis 1a): Among individuals with TBI of >6 months duration and moderate-to-severe irritability, BUSP (15 mg daily dose with titration up to 60 mg daily as needed for irritability control) compared to placebo will result in a statistically significant **greater proportion of responders** as defined by a **decrease of at least 3 points** on the observer-rated Neuropsychiatric Inventory (NPI) Irritability domain scores from baseline to Day 91. **Hypothesis 1b:** Among individuals with TBI of >6 months duration, BUSP (15 mg daily dose with titration up to 60 mg daily) will result in **statistically significant improvement** on scores of one or more of the following measures compared to placebo:

- a) Observer and participant ratings of NPI and NPI-Distress *Irritability* domain scores,
- b) Observer and participant ratings of NPI and NPI-Distress *Aggression* domain scores,
- c) Participant ratings of TBI-QOL Anger bank,
- d) Observer ratings of SASNOS Aggression, subscale,
- e) Observer and participant ratings of Global Impression of Change,
- f) Physician ratings of Clinical Global Impressions.

Secondary Aim: Assess the adverse events of BUSP in treating TBI irritability/aggression.

Hypothesis 2: BUSP will be well-tolerated as measured by number and types of the adverse events in the treatment group compared to the placebo group.

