- **St Andrew's-Swansea Neurobehavioural Outcome Scale (SASNOS):**¹¹⁵ SASNOS is a newly developed informant-rated measure designed specifically to assess neurobehavioral dysfunction in acquired brain injury as rated by an observer. SASNOS has a 5-factor conceptual framework based on the World Health Organization International Classification of Function (WHO ICF) that allows the measurement of a diverse range of NBD signs and symptoms in the following domains: interpersonal relationships, cognition, aggression, inhibition and communication. Initial validation suggests that the 49-item SASNOS is reliable and valid. The proposed study will utilize the aggression subscale, which includes 15 items and three subfactors: overt aggression (3 items), irritability (6 items), and provocative behavior (6 items). The aggression subscale demonstrates excellent test-retest reliability (ICC=.92) and internal consistency (alpha=.92), good inter-rater reliability (ICC=.80), and a strong statistical relationship with known measures, supporting its content, convergent, and divergent validity.

- **Global Impression of Change (GIC):** A Likert Scale rating impression of change (much improved, slightly improved, no change, slightly worse, or much worse) will be used for both participants and observers to rate their impression of change in the person with TBI.

- **Clinical Global Impressions (CGI):** The clinician's impression of change will be determined using the CGI. The CGI¹⁵⁸ is a highly sensitive,¹⁵⁹ standardized assessment tool used widely to assess psychopharmacology treatment response. The CGI is comprised of 3 subscales: Severity of Illness (SI), Global Improvement (GI), and Efficacy Index (EI). SI and GI are both rated on 7-point scales. The EI is rated on a 4-point scale that takes into account both beneficial effects and side effects. The CGI is rated by a clinician/investigator. The SI subscale is administered at initial assessment and then all three subscales are administered at follow-up assessments. To be considered effective, a treatment should lower the overall score in subsequent testing by at least 50%.¹⁶⁰ The CGI takes approximately 2 minutes for the clinician to score.

Experimental Measure (this measure to be developed after study completion, and thus, will be delayed in time from final analysis)

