- **Aggression and Irritability Impact Measure (AIIM):** The AIIM is an experimental measure that will be developed and evaluated through the companion measurement study. It will consist of items assessing the degree to which irritability or aggression interferes with community participation activities. Specific community participation activities will be represented by items of the Participation Assessment with Recombined Tools-Objective (PART-O).¹⁶¹ Additional items may be added after focus group review and cognitive interviewing that will take place prior to launching the study. The AIIM will be designed to assess specifically the degree to which irritability and aggression interfere with participation in contrast to the PART-O which assesses the extent of community participation in general. The beta version of the AIIM will be included in this Buspirone treatment study. It will be administered at the Baseline and Final visits as it is thought that the longer period is needed to allow time for changed impact. After refining it through psychometric studies, the final version of the AIIM will be extracted from the Beta version and analyzed as a dependent measure in the treatment arm to assess its responsiveness to the hypothesized treatment effect. The AIIM is included in the treatment arm only to assess its responsivity and not as an endpoint.

- **Working Alliance Inventory-Short Revised (WAI-SR):** The WAI-SR is a 12 item questionnaire with forms for completion by the person receiving treatment as well as by the provider. This measure of working or therapeutic alliance has been shown to predict the outcome of psychotherapeutic as well as rehabilitation interventions.²¹⁹ The WAI-SR is based on a factor analysis of the full WAI and has demonstrated reliability and validity.²²⁰ The WAI-SR will be completed during the post-treatment assessment session at the end of the buspirone trial by the participant and by the research assistant who worked with the participant in the trial. Each of these individuals will complete the inventory independently without knowledge of each other's responses. Data obtained from the WAI-SR will be evaluated as a covariate in analyses of outcome variables to assess for effects of buspirone relative to placebo.

Stratification Measure

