Demographic and baseline measurements will be compared between the two groups. Variables measured on an interval scale (e.g., age) will be compared between the two groups with a Student's t-test. Variables that are not normally distributed will be tested with the Wilcoxon rank sum test. The chi-square test or Fisher's exact test will be employed for variables measured on the nominal scale (e.g., gender).

Concomitant Medications: Concomitant medications will be summarized.

Participant Disposition: Disposition will be tabulated showing the number of those entered and discontinued for any reason. Reasons for discontinuation will be listed and summarized.

Compliance: Number of subjects who are compliant with respect to pill taking (defined as $\geq 75\%$ of prescribed study medication consumption) will be reported.

Subject Replacements: Subjects who discontinue the study will not be replaced.

Sample Size: The sample size is based on the sample size needed for the primary and secondary efficacy analyses. For the primary outcome (proportion of participants who have a decrease of at least 3 points in their Irritability Domain Score), thirty-three participants per group are necessary to detect a difference of 40% having a successful decrease in irritability in one group versus 80% in the other, using a chi-square test with a power of 90% and an alpha of 0.05. This is the effect size we observed in our prior amantadine single-site study.⁴³ For the secondary outcomes, the sample size for the Wilcoxon rank sum test was calculated using the formulas derived by Noether.¹⁶⁷ Thirty-three people are needed in each group to ensure a power of 80%, with an alpha of 0.05, and $p = \text{probability}(Y > X) = 0.70$, where Y and X are random samples from the two populations (groups). Under the null hypothesis $p = 0.50$. To allow for a 10% loss-to-follow up, 37 participants will be enrolled into each of the 2 study arms for a total sample of 74.

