Available Sample and Back-up Plan to Achieve Recruitment Numbers: Based on several assessments, we expect to recruit according to our timeline as we have in our prior studies. The PI has successfully conducted several similar pharmacologic studies for irritability in this population which have run according to timeline and provided insight to recruitment obstacles and solutions. In two similar single-site studies, the PI was able to enroll 76 participants over 3.5 years with only a 5% drop out rate. A similar study is near completion at IU with enrollment progressing ahead of schedule. We have ample access to the target population to satisfactorily recruit. Recruitment reports are reviewed by the research team monthly and compared to benchmarks. If/when recruitment falls below benchmark, an action plan will be implemented. If recruitment lags behind benchmarks, we will repeat our intense local advertisement efforts (to both clinicians and persons with brain injury), expand the advertisement to nearby communities, expand our recruitment across Indiana, and provide targeted education about our study and irritability in general to clinicians and persons with brain injury across the state. If necessary, we can extend involvement in this study to other PM&R specialists and psychologists in the region or to nearby residential facilities. If for some reason we still lack adequate recruitment, we will discuss potential options with our NIDRR project officer, such as contracting with another center.

Subject participation duration: 131 days (including open-label); **Study Duration:** 5 years.

Efficacy Analyses:

Hypothesis 1a: Among individuals with TBI of >6 months duration and moderate-to-severe irritability, BUSP compared to placebo will result in a statistically significant greater proportion of responders as defined by a decrease of at least 3 points on the observer-rated Neuropsychiatric Inventory (NPI) Irritability domain scores from baseline to Day 91.

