Hypothesis 1b: Among individuals with TBI of >6 months duration, BUSP will result in statistically significant improvement in scores of one or more of the following measures compared to placebo: a) observer and participant ratings of NPI and NPI-Distress Irritability domain scores, b) observer and participant ratings of NPI and NPI-Distress Aggression domain scores, c) participant ratings of TBI-QOL Anger bank, d) observer ratings of SASNOS, e) observer and participant ratings of Global Impression of Change, f) physician ratings of Clinical Global Impressions.

The primary analysis will be intention-to-treat. For Hypothesis 1a, the primary outcome, the percent of participants who are considered to have meaningful reduction in irritability (decrease of at least 3 points in the NPI Irritability Domain Score) from baseline to 91 days, will be compared between the two groups (those receiving active drug and

placebo) using a chi-square test. A logistic regression model will be used to adjust for depression and possible demographic and baseline differences between the two groups and a post-hoc secondary analysis will examine the factors (including depression and anxiety) influencing the effect of BUSP on the primary outcome by including group interaction in the logistic model. For Hypothesis 1b, the change in the observer-rated NPI Irritability Domain Score from baseline to 91 days will be compared between the two groups using a Wilcoxon rank sum (Mann-Whitney) test for ordered categories. The secondary outcomes will also be compared between the two groups using Wilcoxon rank sum tests. For the secondary outcomes, Hochberg's step-up Bonferroni method will be used to control for multiple testing. Secondary analyses will include repeating the analyses above using the PPS population. Wilcoxon rank sum tests will also be performed for separate subgroups such as females, males, participants with injury caused by motor vehicle crashes or falls to test whether BUSP can be efficacious for these separate subgroups. In addition, if a substantial number of participants have depression, a preliminary analysis of the effect of BUSP on PHQ-9 may be performed. The effect of BUSP on GAD-7 will also be performed.

Safety Analysis: Hypothesis 2: BUSP will be tolerated as measured by number and types of the adverse events in the treatment group compared to the placebo group.

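### The 80% power stated for the secondary outcomes is for one unadjusted test; under the planned Hochberg procedure it is about 47–61% per outcome, and the subgroup tests have no multiplicity control

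*Combined protocol and SAP*

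**What the plan says.** Section 8.1 (Sample Size) opens with "The sample size is based on the sample size needed for the primary and secondary efficacy analyses". For the secondary outcomes it uses Noether's formula for the Wilcoxon rank sum test with P(Y>X) = 0.70 against 0.50 under the null: "Thirty-three people are needed in each group to ensure a power of 80%, with an alpha of 0.05". Allowing for 10% loss, 37 per arm (74 in total) are enrolled.

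Section 8.1 (Efficacy Analyses) then says of the secondary outcomes that Hochberg's "step-up Bonferroni method will be used to control for multiple testing". Hypothesis 1b is worded as "statistically significant improvement in scores of one or more of the following measures compared to placebo". The number of outcomes in the Hochberg family is not given.

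The same section plans Wilcoxon tests in separate subgroups, giving females, males, motor vehicle crash injuries and falls as examples, to see whether buspirone can work in each. No multiplicity method is stated for them. Interaction terms are planned only in the logistic model for the primary outcome, and the factors named there are depression and anxiety.

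**The concern.** The power statement and the analysis plan describe different tests. The sample-size paragraph gives the power of one comparison at 0.05. The analysis compares each p-value with a Hochberg threshold that can be as strict as 0.05 divided by the family size. Nothing in the plan allows for the difference.

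If the 80% is taken at face value, a non-significant secondary outcome may be reported as evidence of no effect from a well-powered test when the chance of detecting the assumed effect was much lower.

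The subgroup tests raise a related risk. Significance in one sex and not the other is easily read as a differential effect, although it arises often when the effect is the same in both.

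**Working it through.** **Inputs.** From 8.1: 33 per group (66 analysed), alpha 0.05, P(Y>X) = 0.70, 74 enrolled, Hochberg for the secondary outcomes. From 5.1: 1:1 allocation. Sidedness is not stated; two-sided reproduces the plan's n.

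**The plan's own figure.** Noether, with N the total: N = (z₀.₉₇₅ + z₀.₈₀)² / [12 × 0.25 × (0.70 − 0.50)²] = (1.960 + 0.8416)² / 0.12 = 65.4, hence 33 per group. Power = Φ(0.2√(3N) − 1.960). At N = 66 this is Φ(2.814 − 1.960) = 80.4%; at 70 it is 82.6%; at 74 it is 84.6%. The stated figure reproduces as a single unadjusted test. The 70 case is close to 5% loss from 74, since the plan reports earlier trials "with only a 5% drop out rate".

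**Family size.** Hypothesis 1b (2.1 and 8.1) begins with "Observer and participant ratings of NPI and NPI-Distress" for Irritability and repeats the pattern for Aggression.

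| Item | Outcomes |
|---|---|
| NPI and NPI-Distress × 2 domains × 2 raters | 8 |
| TBI-QOL Anger | 1 |
| SASNOS Aggression | 1 |
| Global Impression of Change × 2 raters | 2 |
| Clinical Global Impressions | 1 |
| **Total** | **13** |

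The total is 12 if the observer NPI Irritability change, which 8.1 describes in its own sentence, is tested outside the family; that outcome would then keep its 80%. It is 15 if the CGI subscales count separately (5.1: "The CGI is comprised of 3 subscales").

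**Floor: one outcome effective, strictest threshold 0.05/m.** Power = Φ(0.2√(3N) − z₁₋₀.₀₂₅/ₘ). For m = 13, z = 2.8905.
- N = 66: Φ(2.814 − 2.8905) = 47.0%
- N = 70: 50.3%
- N = 74: 53.6%
- N = 66 with m = 12: 48.0%; with m = 15: 45.2%

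**Hochberg with more outcomes effective.** Simulated with equicorrelated normal test statistics, 200,000 draws per scenario. The correlation is an assumption: 0.3–0.7, with 0.9 as an extreme. Per-outcome power, 13 outcomes:

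| Analysed | One effective | Six effective | All effective (0.3–0.7) | All effective (0.9) |
|---|---|---|---|---|
| 66 | 47% | 50% | 60–61% | 65% |
| 70 | 50% | 53% | 64–65% | 68% |
| 74 | 54% | 57% | 68% | 71% |

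At 66 analysed, a family of 12 gives 48–62% and a family of 15 gives 45–60% (correlation 0.3–0.7). Simulating actual rank-sum tests with 33 per arm gives about 46–48% with one effective and 61–64% with all 13 effective.

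**At least one success, 13 outcomes, correlation 0.3–0.9.**

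| Analysed | One effective | Six effective | All effective |
|---|---|---|---|
| 66 | 47% | 63–90% | 70–97% |
| 74 | 54% | 69–94% | 76–98% |

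**What 80% at 0.05/13 would take.** P(Y>X) = 0.5 + (2.8905 + 0.8416)/√(3N) = 0.765 at N = 66 and 0.750 at N = 74. At P(Y>X) = 0.70, N = (2.8905 + 0.8416)²/0.12 = 116.1 analysed.

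**Subgroups, same effect in both sexes, 66 analysed.** The proportion male is an assumption.
- 50% male: power is Φ(0.2√99 − 1.960) = 51.2% in each sex, so significance in one sex only has probability 2 × 0.512 × 0.488 = 50%.
- 65% male: 53%.
- 80% male: power is 71.1% in men and 24.2% in women, so 0.711 × 0.758 + 0.289 × 0.242 = 61%.

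Under the null, at least one of the four named subgroup tests is significant in about 16–17% of trials (assuming 30–60% motor vehicle crashes and 20–40% falls).

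**The case against.** The strongest reply is that Hypothesis 1b succeeds on any one measure, so per-outcome power is not its criterion. At correlations of 0.3–0.7 with 66 analysed, the chance of at least one success is 75–90% if six outcomes respond and 83–97% if all do. This is right, and it limits the point to claims about individual outcomes. But the plan does not calculate that power either, and it falls to 47% if only one outcome responds. The stated 80% describes neither quantity.

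The 47% end is a floor. The measures overlap heavily, so a single responder among 13 is not the typical case. That also stands, but even the most favourable scenario run (74 analysed, all effective, correlation 0.9) reaches only 71%.

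The family is not fixed by the text. Twelve is a natural reading, and the list of secondary efficacy measures in 5.1 includes the WAI-SR. The WAI-SR is not in Hypothesis 1b, however, and 5.1 also says "Data obtained from the WAI-SR will be evaluated as a covariate in analyses of outcome variables". Choosing 12 or 15 instead of 13 moves the power by only one or two points. The ambiguity is itself something to settle.

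On subgroups, no confirmatory claim rests on these tests, and the named interaction factors are not presented as a complete list. But those interactions concern the primary outcome only, and the subgroup tests are framed as tests of efficacy within each subgroup and are not labelled exploratory.

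Finally, 33 per group is also what the plan gives for the primary outcome alone, so the sample size does not depend on this calculation. Agreed.

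**Conclusion.** The concern holds. The 80% is the power of one unadjusted test. Under the planned Hochberg procedure over 13 outcomes, power for an individual outcome is about 47–61% with 66 analysed and 54–68% with all 74. This rests on P(Y>X) = 0.70 for the effective outcomes, on between one and all of them being effective, and on correlations of 0.3–0.7; the documents give neither the number effective nor the correlation. Within-subgroup tests without multiplicity control or a matching interaction test invite false contrasts. The primary analysis, the sample size and Hochberg's control of error are not affected.

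**What to change.** In 8.1 (Sample Size), state that 80% is the power of a single unadjusted secondary test. Add the per-outcome power under Hochberg at P(Y>X) = 0.70 with 66 analysed, with its assumptions: about 47% if one outcome is effective, about 61% if all are. Alternatively, state that 80% per outcome needs P(Y>X) of about 0.77. Give the power for at least one success as well.

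In 8.1 (Efficacy Analyses), name the Hypothesis 1b list as the Hochberg family, say whether the observer NPI Irritability change is inside it, and name one CGI subscale. Leave the WAI-SR out as a covariate, and bring the 5.1 list of secondary efficacy measures into line.

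Replace the within-subgroup tests with treatment-by-subgroup interaction tests plus subgroup estimates and 95% confidence intervals, labelled exploratory.

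The cost is a text change and a little more analysis, with no more patients. The stated secondary power will look less favourable, and the interaction tests will themselves have low power at this sample size, which is why they can only be exploratory.

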3.1 INCLUSION/EXCLUSION CRITERIA

INCLUSION CRITERIA
Closed head injury (impaired brain function resulting from externally inflicted trauma without penetrating injury as defined below) at least 6 months prior to enrollment Non-penetrating and meets Mayo Classification ¹⁵⁶ of mild or moderate-severe brain injury with evidence from the medical record, clinician report, or detailed history provided by the participant or family. (Note: Intoxication, sedation, intubation, or use of paralytics must be ruled out as causes of impaired consciousness)
Moderate to Severe (one of more of the following) Loss of consciousness of ≥ 30 minutes Post-traumatic anterograde amnesia of ≥ 24 hours Worst Glasgow Coma Scale full score in first 24 hours < 13 (unless invalidated upon review, e.g., attributable to intoxication, sedation, systemic shock) Intracerebral hematoma, epidural hematoma, cerebral contusion, hemorrhagic contusion, subarachnoid hemorrhage, or brain stem injury
MILD (one of more of the following) Loss of consciousness of momentary to < 30 minutes Post-traumatic anterograde amnesia of momentary to < 24 hours Depressed, basilar or linear skull fracture (dura intact)
Irritability that is either new or worse than level of irritability before the traumatic brain injury, by report of observer or person with TBI
Age at time of enrollment: 18 to 70 years
Voluntary informed consent of patient or guardian or legally-authorized representative and observer
Subject and observer willing to comply with the protocol
Observer-rated NPI Irritability Domain score 6 or greater to include only moderate-severe irritability
Medically and neurologically stable during the month prior to enrollment
If taking antidepressant, anxiolytic, hypnotic, or stimulant medications, no change anticipated in these medications during the month prior to enrollment
No change in therapies or medications planned during the 91-day participation
No surgeries planned during the 91-day participation
Vision, hearing, speech, motor function, and comprehension sufficient for compliance with all testing procedures and assessments

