NPI Irritability domain rated by observer. NOTE: The primary analysis looks at the proportion that decrease ≥ 3 points to assess clinical significance in addition to statistical significance. This cut point of clinically meaningful change is based on clinical experience and

consumer input, and was utilized in our previous studies. A secondary analysis compares changes in NPI-Irritability using an ordinal scale.
Secondary Efficacy Measures
NPI- Irritability domain rated by observer and participant
NPI-Distress Irritability domain rated by observer and participant
NPI & NPI-Distress Agitation/Aggression Domain rated by observer and participant
TBI-QOL Anger item bank rated by participant
SASNOS rated by observer
Global Impression of Change rated by observer and participant
Clinical Global Impressions rated by clinician
Working Alliance Inventory – Short Revised rated by participant and Co-Investigator.

Demographic and Pre-treatment Characteristics: Age, gender, marital status, ethnicity, educational level, time since injury, history of psychiatric disorder, previous TBI, cause of injury, CT scan findings, initial Glasgow Coma Scale score in ED, duration of post-traumatic amnesia (PTA), duration of loss of consciousness, socioeconomic status, employment status, substance use during the month prior to enrollment, relationship of observer to subject, medical history, overall function, severity of irritability, and presence of depression, anxiety or post-traumatic stress disorder (PTSD).

Efficacy Measures:

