- **Neuropsychiatric Inventory (NPI & NPI-Distress):** The NPI¹⁰⁴ is a 40-item tool developed to assess behavioral abnormalities in individuals with dementia. Since its development, the NPI has been used in TBI populations to assess neurobehavioral dysfunction.^{23,43,50} It is a fully structured observer interview that specifies verbatim the questions to be asked. The observer indicates if a specific behavior has been present during the past month or specified time period and if this represents a change from premorbid functioning. The most problematic behavior detected by the sub-questions is then used to grade the frequency and severity: behavior severity (1 = mild, 2 = moderate, 3 = severe) and frequency (1 = occasionally, less than once per week; 2 = often, about once per week; 3 = frequently, several times per week, but less than every day; 4 = very frequently, once or more per day or continuously) and the product (severity x frequency) is calculated (range 0-12). The NPI also assesses the caregiver’s distress over the behaviors on a 6-point scale: 0 (no distress), 1 (minimal), 2 (mild), 3 (moderate), 4 (moderately severe), and 5 (very severe or extreme).

For the present study, we will use the NPI Irritability and Aggression domains as outcome measures. The Irritability domain includes: bad temper, rapid mood changes, sudden anger, impatience, crankiness, argumentativeness. The Aggression domain includes: getting upset, resisting activities, stubborn, uncooperative, hard to handle, shouts, curses angrily, slams doors, kicks furniture, throws things, hurts or hits others.

The NPI has established content and concurrent validity, as well as inter-rater (approximately 95% for both frequency and severity), test-retest (0.79 for frequency and 0.86 for severity), and internal consistency reliability (Cronbach’s alpha of 0.88 for both).¹⁰⁴ The NPI-Distress has established content and concurrent validity, and inter-rater (0.96), test-retest (0.92), and internal consistency reliability.¹⁰⁵

Few scales exist to specifically assess irritability in neurologic disorders. Other available measures ask only about the presence or frequency of irritability. Only the NPI assesses the distress caused by the irritability. This multifaceted assessment of the problem makes the NPI ideal for the study of irritability in TBI, and specifically in this medication trial.

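### The 3-point responder rule on the NPI product score depends on the entry state, yet the primary chi-square uses neither entry NPI nor the PHQ-9 randomisation stratum

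*Combined protocol and SAP*

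**What the plan says.** Section 5.1 (Efficacy Measures) builds the NPI domain score from "behavior severity (1 = mild, 2 = moderate, 3 = severe") and four frequency grades, the highest being "4 = very frequently, once or more per day or continuously". It states that "the product (severity x frequency) is calculated (range 0-12"). Section 3.1 requires "Observer-rated NPI Irritability Domain score 6 or greater to include only moderate-severe irritability".

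Section 8.1 (Efficacy Analyses, Hypothesis 1a) defines response as a "decrease of at least 3 points in the NPI Irritability Domain Score" by Day 91 and compares the two proportions with a chi-square test under intention-to-treat. The Outcome Variables table in Section 5.1 gives the reason for the cut: "The primary analysis looks at the proportion that decrease ≥ 3 points to assess clinical significance in addition to statistical significance". It bases the value of 3 on clinical experience, consumer input and use in earlier studies.

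Three other provisions bear on the point:

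- Section 4.1 stratifies randomisation on PHQ-9 total score (5 or more) and on nothing else.
- Section 8.1 adds a logistic model that adjusts for depression and for possible demographic and baseline differences. Entry NPI is not named.
- Section 8.1 also compares change in the observer-rated NPI Irritability score by a Wilcoxon rank sum test, as a secondary analysis.

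No section discusses how a fixed 3-point cut behaves on a product scale.

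**The concern.** On a product scale, one category of improvement in frequency is worth as many points as the severity grade, and one category in severity is worth as many points as the frequency grade. A fixed 3-point cut therefore asks for different amounts of improvement from participants who enter in different states. Two things follow.

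First, entry score probably predicts responder status strongly. A primary test that omits it gives up some precision, and the estimate is exposed to whatever imbalance in entry score arises by chance with about 37 per arm.

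Second, the responder percentage, which the plan offers as evidence of clinical significance, pools participants who left the trial's own moderate-severe range with participants who did not.

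**Working it through.** **The plan's own figure.** Section 8.1 arrives at 33 per group, for 90% power at the 0.05 level with the chi-square, in order to "detect a difference of 40% having a successful decrease in irritability in one group versus 80% in the other". Two-sided, uncorrected: n = [1.96·√(2·0.6·0.4) + 1.282·√(0.4·0.6 + 0.8·0.2)]² / 0.4² = (1.358 + 0.811)² / 0.16 = 29.4, so 30. With continuity correction it is 35. Exact enumeration at 33 per group gives 90.1% power for the continuity-corrected chi-square and 94.0% uncorrected, so 33 is reproduced. Allowing for loss, 33 / 0.9 = 36.7, so 37. The sample size is not in question.

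**Attainable scores.** Severity 1-3 times frequency 1-4, plus 0 for absent, gives 0, 1, 2, 3, 4, 6, 8, 9 and 12. With entry at 6 or more, the starting scores are 6, 8, 9 and 12.

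**One-category steps from each entry state.**

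| Entry score (severity x frequency) | Severity down one | Frequency down one | Smallest qualifying fall |
|---|---|---|---|
| 6 (2x3) | to 3, response | to 4, no response | 3 points, 50% |
| 6 (3x2) | to 4, no response | to 3, response | 3 points, 50% |
| 8 (2x4) | to 4, response | to 6, no response | 4 points, 50% |
| 9 (3x3) | to 6, response | to 6, response | 3 points, 33% |
| 12 (3x4) | to 8, response | to 9, response | 3 points, 25% |

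From 8 the effective threshold is 4 points, because 5 cannot occur. Every responder from 6 or 8 ends at 4 or below. A responder from 9 can end at 6, and one from 12 at 8 or 9; each of these still meets the entry threshold. The two rows for score 6 show that composition matters as well as the score.

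**How prognostic entry score might be.** The documents give no distribution of entry scores or of category changes, so this is an assumption. Let frequency fall by 0/1/2/3 categories in 55/30/12/3% and severity by 0/1/2 in 75/20/5%, independently and identically for everyone.

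- 2x3 or 2x4 (severity falls at all, or frequency falls by two or more): 1 - 0.75 x 0.85 = 36%.
- 3x2 (frequency falls at all, or severity falls by two): 1 - 0.55 x 0.95 = 48%.
- 9 or 12 (any fall): 1 - 0.55 x 0.75 = 59%.

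**Chance imbalance.** Assume half enter at 9 or 12. The standard deviation of the between-arm difference in that share is √(2 x 0.25 / 37) = 0.116. A difference of 15 points or more then has probability 2 x [1 - Φ(0.15 / 0.116)] = 0.20. Taking 38% response at low entry and 59% at high, a 15-point imbalance moves the responder difference by 0.15 x (0.59 - 0.38) = 3 points. As an extreme case, let everyone improve by exactly one category, with severity and frequency steps equally likely, so that response is 50% from 6 or 8 and 100% from 9 or 12. A 20-point imbalance then moves the difference by 0.20 x 0.50 = 10 points.

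**Type I error.** Simulated under no effect, the plain and the stratified tests both sit at about 5% with 37 per arm. One run at 33 per arm gave 6.0% uncorrected and 4.9% stratified. That excess reflects the discreteness of the uncorrected test: under randomisation and no effect, both arms have the same overall response probability.

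**Power.** The comparison is the plain chi-square, a Cochran-Mantel-Haenszel (CMH) test on two entry-score strata, and a CMH test on four strata (entry score by PHQ-9). Half are assumed to enter at 9-12. For the four-stratum results, 80% are assumed to have PHQ-9 of 5 or more.

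| Responder rates, low/high entry (placebo; active) | n per arm | Chi-square | Two strata | Four strata |
|---|---|---|---|---|
| 38/59%; 70/88% | 37 | 79.4% | 80.9% | 79.9% |
| 38/59%; 75/85% | 37 | 82.6% | 83.6% | 82.3% |
| near the plan's 40% v 80% | 37 | 95.2% | 95.8% | 95.6% |
| 20/60%; 65/95% | 33 | 94.2% | 96.4% | not run |
| 30/50%; 70/90% | 33 | 94.2% | 94.2% | not run |

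Other illustrations at 37 per arm put the gain at 1 to 3 points for either stratified test. Under the 80% assumption, about 43% of simulated trials had at least one of the four strata with fewer than 6 participants.

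**The case against.** The best defence is that nothing here is invalid. Allocation is randomised, responder status is a function of baseline and Day 91 scores, and the chi-square keeps its error rate. Chance imbalance in any prognostic factor is already part of the sampling error, and a shift of about 3 points is small beside a planned 40-point difference. All of this stands. A reader might infer that the primary test is biased, that its type I error is inflated or that the sample size is wrong. The documents and the calculations support none of these.

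The plan is also not blind to baseline. Severity of irritability is a listed pre-treatment characteristic, baseline measurements are compared between arms, the logistic model can adjust for baseline differences, and the Wilcoxon analysis avoids the cut. It would be too strong to say that the plan ignores entry score. What remains is narrower: entry NPI is not named in the model, its inclusion appears to depend on what the baseline comparison shows, and the Wilcoxon analysis still uses raw change in the product.

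Every absolute-change responder rule depends on baseline, and the sponsor has reasons for this one, including comparability with its earlier trials. Nothing in the documents requires a responder to finish below 6, so a responder who still scores 6 or more is not a contradiction. This too stands, and it is why the cut should be kept.

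Finally, stratifying does not make the rule uniform. A 6-8 stratum still pools 2x3, 2x4 and 3x2, and four strata may be thin. Both limits are real.

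**Conclusion.** The point holds as one of precision, chance imbalance and interpretation. It follows by enumeration, with no assumptions, that the 3-point rule accepts any one-category improvement from entry scores 9 and 12 but only one of the two from 6 and 8, and that responders from 9 or 12 can remain at or above the entry threshold. It is also plain from Section 8.1 that the primary test uses neither entry NPI nor the randomisation stratum.

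The size of the effect rests on assumed distributions. In the illustration, identical category changes give responder rates from 36% to 59% depending on entry state. A 15-point imbalance in entry score, expected in about one trial in five, shifts the responder difference by about 3 points. The power gain from stratifying is modest: about 1 to 3 points in most illustrations, close to nil in some, and in one of them the four-stratum test was fractionally below the plain chi-square. The case for the change rests mainly on fixing the adjustment in advance and making the responder percentage readable, at almost no cost.

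**What to change.** Keep the 3-point cut. Before unblinding:

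1. Make the primary Hypothesis 1a test a CMH test stratified by entry observer-rated NPI Irritability score (6-8 versus 9-12) and by the PHQ-9 randomisation stratum.
2. Pre-specify a rule, based on stratum counts alone, for dropping to the two entry-score strata when a combined stratum is sparse (for example, fewer than 6 participants).
3. Name baseline NPI Irritability as a fixed covariate in the planned logistic model, whether or not the arms differ on it.
4. Report responder rates by entry score in each arm.
5. Optionally, add one descriptive row for responders whose Day 91 score is below 6.

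The cost is a few lines of SAP text and code; all the data are already collected. Section 8.1 asks for an amendment when a significant protocol feature changes, and a new primary test would reasonably count as one. The downsides are a slightly more complex primary table and possible sparse strata. The change does not make the 3-point rule uniform across entry states; reporting by entry score lets readers see the difference.
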